**6. Statistical Analysis and Method of Data Analysis**

All data will be summarized with descriptive stats (number of subjects, mean, standard deviation, minimum, median, and maximum) for continuous endpoints and frequency and percentage for categorical endpoints.

The differences between outcome measures in the doxycycline group versus the placebo group will be contrasted using Student's t-test for each of the primary and secondary outcome measures. If the outcome measurements do not meet the normality assumption even after a transformation, non-parametric approach of Wilcoxon sign-rank tests can be used to test the differences between doxycycline and placebo. Although we will have enough washout time before cross over to other treatment arm, we can test the effects of sequence and carryover in a model.

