The potential of doxycycline to suppress angiogenesis and reduce nosebleeds has been previously recognized and studied in a pilot study (22). A retrospective analysis of seven HHT patients treated with oral doxycycline demonstrated that epistaxis severity score (ESS) significantly decreased with treatment, from a pre-treatment ESS of 4.9 to a post-treatment ESS of 2.6. This almost 50% reduction in nosebleed severity underscores the anti-angiogenic properties of doxycycline and supports the potential of this therapy in HHT.

The NOSTRIL study will be the first prospective, randomized trial to assess the control of epistaxis in HHT with prophylactic doxycycline. This therapy has the potential to dramatically improve the health and quality of life of patients with HHT.

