### **3. Study Design and Dose Rationale**

#### **a. Study Design Rationale**

A randomized (1:1), prospective, cross-over design will be used. This guarantees that all participants will receive treatment with the treatment drug, which is important since all patients enrolled will have significant epistaxis and desire treatment. An identical design was used in a previous study of epistaxis reduction in HHT patients (23).

A one-month wash-out period between placebo and treatment drug was selected based on doxycycline pharmacokinetics and mucosa turnover rate. Doxycycline is almost completely absorbed orally with bioavailability of 95% and a time to peak concentration of about 3 hours. The half-life of the drug is about 14 hours, with elimination in both the urine and stool. Thus, the drug will be almost completely absent one week after the last dose (12 half-lives). The nasal mucosa, which could be affected by the drug, regenerates approximately every 5 days (24). Thus the biologic effect of the drug should be virtually absent by 12 days after the last dose. To ensure complete clearance of the drug and its effects between therapy and placebo, an additional two weeks were added, making a total one-month wash-out period.

Subjects who cannot present in person to the clinic due to the COVID-19 virus will conduct the follow-up visit over the phone.

Based on preliminary data (14) the average epistaxis severity score (ESS) for the patients we will recruit is  $4.9 \pm 2.2$ . The preliminary study found that doxycycline treatment reduced the ESS by an average of  $2.4 \pm 1.2$  points. Thus, a sample size of 20 patients from the cross over design will achieve 90% power to test the mean differences in ESS between doxycycline and placebo at alpha of 5% using a two-sided t-test. To consider the possible dropout or missing (approximately 10% rate), a total sample size of 22 patients will be randomized. This was the same sample size used in the previous cross-over trial of a different medication in HHT patients with epistaxis (23).

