#### **a. Study Design:**

- i. This is a single-center, prospective, randomized (1:1), controlled, cross over, double-blinded study
- ii. Total N = 22 Patients
- iii. The following information will be collected during the study:
  - 1- Demographic information

This document is property of [name]/UCLA Medical Center and shall not be reproduced, distributed, disclosed, or used for manufacture or sale of apparatus without the expressed written consent of the University of California, Los Angeles.

- 2- Medical history
- 3- Physical Examination
- 4- Concomitant medication
- 5- Adverse events
- 6- Vital signs
- 7- SF-12 quality of life questionnaire
- 8- ESS score
- 9- Labs

iv. Eligible patients will have a diagnosis of definite HHT by the Curacao criteria or a positive DNA test for HHT (relevant mutation in the genes coding for SMAD-4, ALK-1, or endoglin). Other inclusion criteria include age 18 or older, avoidance of other experimental therapies during the trial, and significant epistaxis (minimum of 3 bleeding episodes per week, total duration of nosebleeds at least 15 minutes per week). Female patients with childbearing potential will require a negative pregnancy test on Day 1 of the trial and at the Crossover visit. Female patients with childbearing potential will also agree to use birth control during the study from Day 1 of the trial (First and Second arm) and for 28 days following cessation of the study medications (Placebo and Doxycycline). Patients will also be excluded if they have used certain medications within 14 days prior to the study, including barbiturates, tegretol, dilantin, warfarin, isotretinoin, and a variety of other medications that are contra-indicated with doxycycline use.

v. Consented subjects will be randomized and blinded to the study medications. Subjects will be randomized to either the Doxycycline arm (100mg PO BID) or to the placebo arm (2 placebo pills/day). After randomization, subjects will have 15 days to 1 month run in period to establish baseline characteristics (bleeding) prior to treatment initiation. As this is a crossover study, subjects will start with one treatment for 2 months followed by a 1 month washout period and then switch to the second treatment for another 2 months and a 1 month follow-up visit.

vi. Both Doxycycline and placebo drugs will be dispensed by the Ronald Reagan UCLA Medical Center (RRUMC) investigational pharmacy. The exploratory grant is covering for the cost of the drugs.

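### The treatment comparison planned for this two-period crossover (t-test with signed-rank fallback) has no period term

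*Combined protocol and SAP*

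**What the plan says.** Section 4.a describes the design: "This is a single-center, prospective, randomized (1:1), controlled, cross over, double-blinded study". Its item v gives the layout: "subjects will start with one treatment for 2 months followed by a 1 month washout period and then switch to the second treatment". Each patient therefore has one treatment in period 1 and the other in period 2, about three months apart.

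Section 6 names the treatment comparison: "The differences between outcome measures in the doxycycline group versus the placebo group will be contrasted using Student's t-test". It applies to each primary and secondary outcome. If normality fails even after transformation, a "non-parametric approach of Wilcoxon sign-rank tests can be used to test the differences between doxycycline and placebo". The only model mentioned is optional: "we can test the effects of sequence and carryover in a model".

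The sample size is in section 3.a: "a sample size of 20 patients from the cross over design will achieve 90% power to test the mean differences in ESS", two-sided at 5%. It rests on an ESS of 4.9 ± 2.2 and a reduction of 2.4 ± 1.2.

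**The concern.** In a two-period crossover, treatment and period are separated only by comparing the two sequences. Section 6 compares doxycycline with placebo directly. The signed-rank fallback suggests that a paired t-test is meant, so adding the word paired would be only a clarification. A paired test still pools both sequences as if period made no difference.

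A period shift is plausible, although the documents give no figure for it. Section 4.c selects patients on at least moderate ESS in the observation month, so drift after entry is possible. Section 3.a allows telephone follow-up because of COVID-19, which may fall unevenly across periods. The washout argument in section 3.a concerns drug clearance and mucosal regeneration. It addresses carryover, not change over time.

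Two things follow from a shift. It enters the error variance, which widens the interval. If the sequences end with unequal numbers of completers, it also moves the estimate and can push type I error at that split above 5%.

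**Working it through.** **Inputs.** From section 3.a: planned effect 2.4, SD 2.2, SD of change 1.2 (the ± figures are unlabelled and read as SDs), 20 completers, two-sided 5%. Assumed: period shift *p* of 0.5 to 1.5 ESS points, the completer split, and the within-patient correlation *r*.

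**1. The plan's own figure.** With *r* = 0 the SD of the within-patient difference is 2.2 × √2 = 3.11. The noncentrality is 2.4 / (3.11/√20) = 3.45, and with 19 df the power is 90.5%; 20 is the smallest N that reaches 90%. The stated 20 patients and 90% therefore reproduce for a paired t-test with *r* = 0 and no period shift.

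**2. Range for the SD of the difference.** The two SDs in section 3.a imply *r* = 1 − 1.2²/(2 × 2.2²) = 0.85. The 1.2 is a before-after figure, apparently from the series described in section 1.a: "A retrospective analysis of seven HHT patients treated with oral doxycycline". The range used is 3.11 (*r* = 0), 2.20 (*r* = 0.5), 1.70 (*r* = 0.7) and 1.20 (*r* = 0.85).

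**3. Equal sequences (10/10).** The doxycycline-minus-placebo difference is centred at effect − *p* in one sequence and effect + *p* in the other. There is no bias, but the sample variance gains *p*² × 20/19. Interval inflation is √(1 + *p*² × (20/19)/SD²).

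| SD of difference | *p* = 0.5 | *p* = 1.5 |
|---|---|---|
| 3.11 | 1.01 | 1.12 |
| 2.20 | 1.03 | 1.22 |
| 1.70 | 1.04 | 1.35 |
| 1.20 | 1.09 | 1.63 |

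In patients, 20 × (1 − 1/inflation²) gives about 1.0, 1.7 and 3.1 of 20 lost at *p* = 0.5 for SDs of 2.2, 1.7 and 1.2.

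Power at 2.4 points, paired against period-adjusted:
- SD 3.11: 90.0% v 90.3% (*p* = 0.5) and 85.9% v 90.4% (*p* = 1.5).
- SD 2.2: 98.6% v 99.6% (*p* = 1.5).
- SD 1.7 or less: both 99.9% or more.

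**4. Unequal sequences.** Bias = *p* × (n₁ − n₂)/20.
- 11/9: 0.5 × 2/20 = 0.05 to 1.5 × 2/20 = 0.15 points.
- 13/7: 0.5 × 6/20 = 0.15 to 1.5 × 6/20 = 0.45 points.

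The period-adjusted estimate has no bias at any split.

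**5. Type I error at a given split** (simulation, no treatment effect). Up to 12/8 the paired t-test is at or below about 5%. Beyond that:

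| Split, shift | SD 3.11 | SD 2.20 | SD 1.70 | SD 1.20 |
|---|---|---|---|---|
| 13/7, 0.5 | 5.2% | 5.3% | 5.7% | 6.2% |
| 13/7, 1.5 | 6.5% | 7.2% | 7.4% | 7.0% |
| 14/6, 0.5 | 5.6% | 6.1% | 7.0% | 8.6% |
| 14/6, 1.5 | 9.5% | 12.5% | 15.2% | 18.7% |

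The period-adjusted t-test stays at about 5% in every cell. The signed-rank test behaves like the paired t-test: 6.6% to 7.2% at 13/7 with a 1.5-point shift, for SDs of 2.2 to 1.2.

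**6. How likely such a split is.** Allocation is stated as 1:1 and no blocking is stated. If randomisation were simple, Binomial(20, 0.5) gives 26% for 13/7 or worse and 12% for 14/6 or worse. Averaged over all splits, the paired type I error is 5.0% to 5.1%.

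**The case against.** The strongest reply is that the planned test keeps its size overall and loses little. Averaged over simple randomisation, type I error is about 5%. With a 0.5-point shift and equal sequences, power at the planned effect falls by 0.3 percentage points at most. A shift of 1.5 points is over 60% of the planned effect and has no source in the documents. If allocation were balanced 11/11 and two patients dropped out, the worst completer split would be 11/9, where bias is 0.05 to 0.15 points and type I error is below 5%. All of this stands, and it is why the point is one of modest size. It does not remove the loss of precision, or the bias at the split obtained. The 2.4-point effect also comes from an uncontrolled retrospective series. At an illustrative effect of 1.0 point with SD 1.2 and 10/10, paired against adjusted power is 92% v 94%, 82% v 94% and 63% v 94% for shifts of 0.5, 1.0 and 1.5.

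A second reply is that the optional model could already be the adjustment. In a model of doxycycline-minus-placebo differences, the sequence coefficient is the period effect. That is true, but section 6 does not give the model's form, does not commit to it and does not make it the treatment comparison. The t-test remains the stated method.

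A third is that adjustment has its own price when there is no shift and the sequences are unequal. That also stands; the figures are given with the fix.

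**Conclusion.** The concern holds. Section 6 sets a treatment comparison without a period term for every outcome of a two-period crossover, and nothing elsewhere in the document supplies one. The consequence is modest and depends on a period shift that has to be assumed. With equal sequences it is lost precision only. With unequal sequences it is also bias, and from 13/7 onwards a type I error above 5% at that split. The 26% and 12% chances of such splits assume simple randomisation, and the largest figures combine a 1.5-point shift with the 1.2 SD. The claim concerns the estimate, interval and test at the split the trial actually obtains. It does not say that the procedure is invalid on average. The change should be made before unblinding.

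**What to change.** In section 6, make the main analysis of each continuous outcome a within-patient analysis with a period effect: a mixed model with fixed treatment, period and sequence and a random patient effect. For patients with both periods, the equivalent is a two-sample t-test between sequences on the period-1 minus period-2 differences. For outcomes that stay non-normal, replace the signed-rank test by a Wilcoxon rank-sum test between sequences on the same differences. The completer version uses the same patients as the paired test. The mixed model would also take in patients with one period only, so state which set is fitted.

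The cost is one paragraph, no new data and one degree of freedom:
- No shift, 10/10, SD 3.11: power at 2.4 points goes from 90.5% (19 df) to 90.3% (18 df), so the planned 20 stands.
- No shift, unequal sequences: the adjusted interval is wider than the paired one by 1% at 11/9, 5% at 13/7 (power 87.5% at SD 3.11) and 10% at 14/6 (84.8%).
- Exact rank-sum in place of signed-rank, no shift, 10/10, SD 3.11: power goes from 88.9% to 87.0%.

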**b. Outcomes**

The primary outcome measures will be the frequency and duration of epistaxis as determined by a nosebleed diary and the Epistaxis Severity Scale (ESS), a validated objective measure of epistaxis severity. The ESS metric has been recommended for the evaluation of new epistaxis therapies. There will also be a number of secondary measures. First, we will evaluate patient quality of life using the objective Short Form-12 (SF-12) Health Status Questionnaire. Laboratory markers of bleeding will represent an additional secondary outcome measure and include ferritin, hemoglobin, hematocrit and MMP-9. To evaluate for severe bleeding requiring transfusion, we will quantify the units of packed red blood cells (PRBCs) transfused over each one-month period of observation. Finally, we will evaluate for treatment failure, including need for nasal surgery or other epistaxis treatments.

c. Inclusion/Exclusion Criteria

i. Inclusion Criteria

- Age 18 and older
- Diagnosis of definite HHT by the Curacao criteria or positive genetic test for HHT
- Epistaxis severity during the observation month is at least moderate by Epistaxis Severity Score (ESS) evaluation, a validated objective index of bleeding severity
- Female patients with childbearing potential will require a negative pregnancy test on the first day of the trial and at the crossover visit. They will also agree to use birth control during the study medication period (placebo and Doxycycline) and for 28 days post study medication intake. This is due to the fact that doxycycline is a Pregnancy Category D medication and since this is a double blinded study, patients need to be on birth control on both arms

ii. Exclusion Criteria

- Patients will be disqualified for use of certain medications within 14 days prior to the study, including barbiturates, tegretol, dilantin, warfarin, isotretinoin, and several other medications that are contra-indicated with doxycycline use.

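### The comparison has no period term, and the sequence and carryover effects it proposes to test cannot be separated from the two period outcomes; a null carryover result would be weak support for the washout

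*Combined protocol and SAP*

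**What the plan says.** Section 4.a sets out a two-sequence, two-period crossover: "subjects will start with one treatment for 2 months followed by a 1 month washout period and then switch to the second treatment" for a further two months. A run-in of 15 days to one month comes after randomisation and before treatment. Section 4.c makes ESS in that month an eligibility criterion ("Epistaxis severity during the observation month is at least moderate by Epistaxis Severity Score (ESS) evaluation"), so a pre-treatment ESS should exist for every patient.

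Section 6 plans a Student's t-test of doxycycline against placebo for each primary and secondary outcome, with a Wilcoxon signed-rank test as fallback. No period term is mentioned. The section ends by saying that the washout is long enough but "we can test the effects of sequence and carryover in a model". It gives no model terms, no time points, no test level and no consequence of either result. It does not say whether run-in ESS enters the model.

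The washout is defended elsewhere. Section 3.a argues it from the drug's half-life and from mucosal regeneration, and then says "an additional two weeks were added, making a total one-month wash-out period". The same section sizes the trial on the treatment difference alone: "a sample size of 20 patients from the cross over design will achieve 90% power".

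**The concern.** The closing sentence of Section 6 offers tests of two effects that the two period outcomes cannot tell apart. What can be estimated from them is a comparison between small groups of different patients, without the within-patient precision that motivates a crossover.

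Two things are at stake.

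- **Reading of a null result.** Carryover of benefit from doxycycline into a later placebo period pulls the treatment estimate towards zero by half its size. At within-patient correlation 0, a 1.2-point carryover would cut the power of the treatment test from 90% to 69%. A non-significant carryover test might be taken as reassurance when it carries little information.
- **The main comparison.** Without a period term, any change in bleeding between the two periods goes into the error. If the sequences end with unequal numbers, part of it also goes into the treatment estimate.

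**Working it through.** **Inputs.** Section 3.a gives ESS 4.9 ± 2.2, a reduction of 2.4 ± 1.2, 20 patients for analysis, 22 randomised, 90% power and two-sided 5%. The ± values are read as SDs; the protocol does not say. Allocation is 1:1, so 10 per sequence is assumed. The within-patient correlation r is not given, so the range 0 to 0.85 is used. The upper end is what the two SDs imply: 1 − 1.2²/(2 × 2.2²) = 0.851.

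**The plan's own figure.** At r = 0 the SD of a within-patient difference is 2.2 × √2 = 3.11. With n = 20, SE = 3.11/√20 = 0.696 and 2.4/0.696 = 3.45. Power is 0.905 on 19 df, and 20 is the smallest n that reaches 90%. The stated figure reproduces at r = 0.

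**Aliasing.** Write μ for the mean, π for period, τ for treatment, σ for a shift of the second sequence and λ for carryover of doxycycline into period 2.

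| Sequence | Period 1 | Period 2 |
|---|---|---|
| Doxycycline first | μ + τ | μ + π + λ |
| Placebo first | μ + σ | μ + π + τ + σ |

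The design matrix has rank 4 for 5 parameters. The patient totals differ between sequences by λ − 2σ, so only that combination is seen. Adding the run-in means, with a period term for them, gives rank 6 for 6 parameters. Sequence and carryover then become separable, provided any sequence difference is the same at run-in as later.

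**Precision of the contrast of totals (σ taken as 0).** SE = 2.2 × √(2(1 + r)) × √(2/10), with 18 df and t = 2.101.

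- r = 0: SE 1.391, half-width 2.92.
- r = 0.85: SE 1.893, half-width 3.98.

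Power is 9 to 13% for a carryover of 1.2 points and 22 to 37% for 2.4.

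**With run-in ESS as covariate (σ still 0).** The residual variance of the total is 2.2² × (2 + 2r − 4r²), with 17 df, t = 2.110 and a small-sample covariate factor √(1 + 1/16) = 1.031. Half-width = 2.110 × 1.031 × √(residual variance × 2/10).

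| r | Half-width by formula | Simulated mean |
|---|---|---|
| 0 | 3.03 | 2.98 |
| 0.25 | 3.21 | 3.16 |
| 0.5 | 3.03 | 2.98 |
| 0.7 | 2.57 | 2.53 |
| 0.74 | 2.43 | 2.39 |
| 0.85 | 1.93 | 1.90 |

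An estimate of zero would exclude a 2.4-point carryover from about r = 0.74. Nowhere in the range would it exclude 1.2. Power is about 12 to 24% for 1.2 and 32 to 70% for 2.4.

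**Both effects left free.** The contrast is the total minus twice the run-in ESS, with SE = 2.2 × √(6(1 − r)) × √(2/10). The half-width is 5.06 at r = 0 and 1.96 at r = 0.85.

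**Period term.** The unadjusted mean of within-patient differences takes in (n₁ − n₂)/N of any period difference. With 11 and 9 completers this is 2/20 = 0.1. With 12 and 8 it is 4/20 = 0.2, but that needs more imbalance than two dropouts from an 11/11 split. At 10 and 10 there is no bias, but the period difference inflates the error. With a 2-point period difference the expected SD of the differences rises from 3.11 to √(9.68 + 4 × 20/19) = 3.73. Simulated power is then about 81 to 82%, against 90% when period is fitted. The period-adjusted estimate has SE = ½ × 3.11 × √(1/10 + 1/10) = 0.696, the same as above. With no period effect its power is 90.3% on 18 df, against 90.5% unadjusted.

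**The case against.** The closing sentence is permissive, the washout is argued separately on pharmacology, and the planned treatment comparison does not depend on the carryover test. All of that stands. The absence of a rule against misusing the test is missing detail, not an error.

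It can also be said that randomisation makes the true sequence effect zero, so the contrast of totals is a carryover test. That is fair, but then there is one effect to test, not two, and the contrast is still imprecise.

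The stakes depend on correlation. At r = 0.85, the treatment test keeps about 99% power even if the whole 2.4 points carried over. That carryover is an upper benchmark, and nothing in the protocol predicts it.

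A reader might infer four stronger claims that the documents do not support.

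- **The washout is too short.** Nothing here shows that.
- **The test will be used to vindicate the washout or to switch analyses.** No section says so.
- **No carryover analysis could support the washout.** With run-in ESS as a covariate and r of about 0.74 or more, an estimate of zero would exclude 2.4 points.
- **The check is least informative where carryover costs most.** This fails for the contrast of totals, which is most precise at r = 0. It is not exact for the covariate analysis either, whose widest interval is near r = 0.25.

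**Conclusion.** The point holds and is minor. The aliasing is algebra, needs no assumed SD and applies to every outcome. The precision figures are for ESS only, because the plan gives no SD for diary frequency or duration, which are also primary. They rest on SD 2.2, 10 per sequence and r between 0 and 0.85. With all 22 patients they narrow slightly (2.8 to 3.8 from totals, 1.8 to 3.0 with the covariate), and the conclusion is the same.

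From the totals, the interval's half-width exceeds the assumed treatment effect at every correlation considered. Adjusting for run-in ESS helps materially only when correlation is high. The likely harm is a missed benefit or false reassurance about the washout: carryover of benefit does not create a false positive. The missing period term is a separate and more practical gain, because fitting it costs almost nothing.

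**What to change.** Replace the last sentence of Section 6 with wording such as:

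> *The primary comparison is the within-patient doxycycline-minus-placebo difference adjusted for period, obtained by comparing period differences between the two sequences. It does not depend on any test of sequence or carryover. If carryover is examined, the analysis will adjust for run-in ESS and report the estimate with its 95% confidence interval. Sequence and carryover will not be tested as separate effects from the two period outcomes.*

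The opening of the t-test paragraph and the non-parametric fallback should be aligned with this.

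The cost is a few lines of text and one degree of freedom. Sample size, data collection, treatment periods and washout are unchanged. Freedom from carryover would still rest mainly on the pharmacological argument in Section 3.a, and any carryover estimate will be imprecise unless within-patient correlation is high.
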